**12.12.2 Definition of SAE**

If an event is not an AE per definition above, then it cannot be an SAE even if serious criteria are met (e.g., hospitalization for signs/symptoms of the disease under study, death due to progression of disease).

An SAE is defined as any untoward medical occurrence that, at any dose:
a. Results in death
b. Is life-threatening The term 'life-threatening' in the definition of 'serious' refers to an event in which the patient was at risk of death at the time of the event. It does not refer to an event, which hypothetically might have caused death, if it were more severe.
c. Requires inpatient hospitalization or prolongation of existing hospitalization In general, hospitalization signifies that the patient has been detained (usually involving at least an overnight stay) at the hospital or emergency ward for observation and/or treatment that would not have been appropriate in the physician's office or outpatient setting. Complications that occur during hospitalization are AEs. If a complication prolongs hospitalization or fulfills any other serious criteria, the event is serious. When in doubt as to whether "hospitalization" occurred or was necessary, the AE should be considered serious. Hospitalization for elective treatment of a pre-existing condition that did not worsen from baseline cannot be considered an SAE because such an event would not constitute an AE.
d. Results in persistent disability/incapacity 
 
• The term disability means a substantial disruption of a person's ability to conduct normal life functions
 
• This definition is not intended to include experiences of relatively minor medical significance such as uncomplicated headache, nausea, vomiting, diarrhea, influenza, and accidental trauma (e.g., sprained ankle) which may temporarily interfere with or prevent everyday life functions but do not constitute a substantial disruption
 

e. Is a congenital anomaly/birth defect
f. Other situations: 
 
• Medical or scientific judgment should be exercised in deciding whether SAE reporting is appropriate in other situations such as important medical events that may not be immediately life-threatening or result in death or hospitalization but may jeopardize the patient or may require medical or surgical intervention to prevent one of the other outcomes listed in the above definition. These events should usually be considered serious
 
 
Examples of such events include invasive or malignant cancers, intensive treatment in an emergency room or at home for allergic bronchospasm, blood dyscrasias or convulsions that do not result in hospitalization, or development of drug dependency or drug abuse.

Abbreviations: AE=adverse event; SAE=serious adverse event.

**12.12.3 Recording and Follow-Up of AE and/or SAE**

AE and SAE Recording

 
• When an AE/SAE occurs, it is the responsibility of the investigator to review all documentation (e.g., hospital progress notes, laboratory reports, and diagnostics reports) related to the event
 
• The investigator will then record all relevant AE/SAE information in the eCRF
 
• It is not acceptable for the investigator to send photocopies of the patient's medical records to the sponsor in lieu of completion of the sponsor/AE/SAE CRF page
 
• There may be instances when copies of medical records for certain cases are requested by the sponsor. In this case, all patient identifiers, except for the patient number, will be redacted on the copies of the medical records before submission to the sponsor
 
• The investigator will attempt to establish a diagnosis of the event based on signs, symptoms, and/or other clinical information. Whenever possible, the diagnosis (not the individual signs/symptoms) will be documented as the AE/SAE.
 

Assessment of Intensity

The investigator will assess the intensity for each AE and SAE reported during the study and assign it to one of the following categories:
 
 
• Mild: An event that is easily tolerated by the patient, causing minimal discomfort and not interfering with everyday activities
 
• Moderate: An event that causes sufficiently discomfort and interferes with normal everyday activities
 
• Severe: An event that prevents normal everyday activities. An AE that is assessed as severe should not be confused with a SAE. Severe is a category utilized for rating the intensity of an event; and both AEs and SAEs can be assessed as severe
 
 
An event is defined as 'serious' when it meets at least 1 of the predefined criteria as described in the definition of an SAE, NOT when it is rated as severe.

Assessment of Severity (toxicity grade)

The toxicity grade of AEs will be graded according to the NCI-CTCAE version 5 of 27 NOV 2017 using the following definitions:
 
 
• Grade 1: Mild; asymptomatic or mild symptoms; clinical or diagnostic observations only; intervention not indicated
 
• Grade 2: Moderate; minimal; local or non-invasive intervention indicated; limiting age-appropriate instrumental activities of daily living (refers to preparing meals, shopping for groceries or clothes, using the telephone, managing money, etc.)
 
• Grade 3: Severe or medically significant but not immediately life-threatening; hospitalization or prolongation of hospitalization indicated; disabling; limiting self-care activities of daily living
 
• Grade 4: Life-threatening consequences; urgent intervention indicated
 
• Grade 5: Death related to AE
 

**Assessment of Causality**

- The investigator is obligated to assess the relationship between study treatment and each occurrence of each AE/SAE
- A "reasonable possibility" of a relationship conveys that there are facts, evidence, and/or arguments to suggest a causal relationship, rather than that a relationship cannot be ruled out
- The investigator will use clinical judgment to determine the relationship
- Alternative causes, such as underlying disease(s), concomitant therapy, and other risk factors, as well as the temporal relationship of the event to study treatment administration will be considered and investigated
- The investigator will also consult the IB and/or SmPC/ PI, for marketed products, in his/her assessment
- For each AE/SAE, the investigator **must** document in the medical notes that he/she has reviewed the AE/SAE and has provided an assessment of causality
- There may be situations in which an SAE has occurred, and the investigator has minimal information to include in the initial report to the sponsor. However, it is **very important that the investigator always make an assessment of causality for every event before the initial transmission of the SAE data** to the sponsor
- The investigator may change his/her opinion of causality in light of follow-up information, and update the CRF documentation accordingly. For SAEs, a follow-up report with the updated causality assessment should be sent
- The causality assessment is one of the criteria used when determining regulatory reporting requirements

**Follow-up of AEs and SAEs**

- The investigator is obligated to perform or arrange for the conduct of supplemental measurements and/or evaluations as medically indicated or as requested by the sponsor to elucidate the nature and/or causality of the AE or SAE/AESI as fully as possible. This may include additional laboratory tests or investigations, histopathological examinations, or consultation with other health care professionals
- If a patient dies during participation in the study or during a recognized follow-up period, the investigator will provide the sponsor with a copy of any post-mortem findings including histopathology
- New or updated information will be recorded in the originally completed eCRF
- The investigator will submit any updated SAE/AESI data to the sponsor within 24 hours of receipt of the information

Abbreviations: AE=adverse event; AESI=adverse event of special interest; ECG=electrocardiogram; eCRF=electronic case report form; IB=Investigator's Brochure NCI-CTCAE; National Cancer Institute-Common Terminology Criteria for Adverse Events; SAE=serious adverse event; SmPC=Summary of Product Characteristics; PI=Product Information.

**12.12.4 Reporting of SAEs/AESIs**

SAE Reporting to the Sponsor via an Electronic Data Collection Tool

 
• The primary mechanism for reporting an SAE/AESI to the sponsor will be the eCRF
 
• If the electronic system is unavailable for more than 24 hours, then the site will use the paper SAE/AESI data collection tool (see below)
 
• The site will enter the SAE/AESI data into the electronic system as soon as they become available
 
• After the study is completed at a given site, the electronic data collection tool will be taken off-line to prevent the entry of new data or changes to existing data
 
• If a site receives a report of a new SAE/AESI from a study patient or receives updated data on a previously reported SAE/AESI after the electronic data collection tool has been taken off-line, then the site can report this information on a paper SAE/ AESI form (see below)
 
• Contacts for SAE/AESI reporting can be found in the Investigator Site File
 

SAE Reporting to Sponsor via Paper Reporting Form

 
• The SAE/AESI paper Reporting Form should be transmitted by email or facsimile
 
• Contacts for SAE/AESI reporting can be found in the Investigator Site File
 

Abbreviations: AESI=adverse event of special interest; SAE=serious adverse event; eCRF=electronic case report form.

## 12.13 Appendix 13: Contraceptive Guidance and Collection of Pregnancy Information

### 12.13.1 Definitions

#### *12.13.1.1 Female of Childbearing Potential (FCBP)*

A woman is considered fertile following menarche and until becoming post-menopausal unless permanently sterile (see below).

If fertility is unclear (e.g., amenorrhea in adolescents or athletes) and a menstrual cycle cannot be confirmed before first dose of investigational medicinal product (IMP), additional evaluation should be considered.

#### *12.13.1.2 Female in the Following Categories Are Not Considered FCBP*

- Premenopausal with 1 of the following:
  - Documented hysterectomy
  - Documented bilateral salpingectomy
  - Documented bilateral oophorectomy
- Postmenopausal
  - A postmenopausal state is defined as no menses for 12 months without an alternative medical cause
  - A high follicle stimulating hormone (FSH) level in the postmenopausal range may be used to confirm a postmenopausal state in women not using hormonal contraception or hormonal replacement therapy (HRT). However, in the absence of 12 months of amenorrhea, a single FSH measurement is insufficient
  - Females on HRT and whose menopausal status is in doubt will be required to use one of the non-hormonal highly effective contraception methods if they wish to continue their HRT during the study. Otherwise, they must discontinue HRT to allow confirmation of postmenopausal status before study enrollment

For individuals with permanent infertility due to an alternate medical cause other than the above, (e.g., Mullerian agenesis, androgen insensitivity, Genetic abnormality like Turner syndrome), investigator discretion should be applied to determining study entry.

Note: Documentation can come from the site personnel's: review of the subject's medical records, medical examination and/or investigation, or medical history interview.

## 12.13.2 Contraception Guidance

### 12.13.2.1 Male Patients

Male patients with female partners of childbearing potential are eligible to participate if they agree to ONE of the following during the protocol-defined time frame [Section 6.1](#) on inclusion criteria

- Are abstinent from penile-vaginal intercourse as their usual and preferred lifestyle (abstinent on a long term and persistent basis) and agree to remain abstinent
- Agree to use a male condom plus partner use of a contraceptive method with a failure rate of < 1% per year as described in [Table 13-1](#) when having penile-vaginal intercourse with a woman of childbearing potential who is not currently pregnant

Men with a pregnant or breastfeeding partner must agree to remain abstinent from penile-vaginal intercourse or use a male condom during each episode of penile penetration during the time period indicated in [Section 6.1](#) on inclusion criteria

Refrain from donating sperm during the same time period.

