### **Applicable in the US:**

- e. Not be pregnant as confirmed by pregnancy tests performed before treatment initiation, within 10–14 days and again within 24 hours of initiating treatment (even if true abstinence is the chosen method of birth control)
- f. Refrain from breast feeding and donating oocytes during the study and for 3 months after the last dose of study drug, or according to US guidelines for LEN, whichever is longer
- g. Agree to ongoing pregnancy testing during the study (every 4 weeks in women with regular menstrual cycle and every two weeks in women with irregular menstrual cycle), and after study therapy has ended (even if true abstinence is the chosen method of birth control). This includes pregnancy testing and counseling if a patient misses her period or if there is any abnormality in her menstrual bleeding
- h. Not get pregnant while taking the study treatment and for at least 3 months after the last dose of study treatments by using at the same time 2 effective methods of contraception, at least one highly effective method and one additional effective method (see [Appendix 13: Contraceptive Guidance and Collection of Pregnancy Information](#)), each time engaging in sexual activity with a male, starting at least 4 weeks before taking the study treatment, while taking the study treatment, during breaks (dose interruptions) and for at least 3 months after stopping the study treatment, or for LEN, according to the US guidelines, whichever is longer. True abstinence from heterosexual sexual intercourse is also an acceptable method of contraception. The use of emergency contraception is also permitted

8. Due to teratogenic potential of lenalidomide, male participants must follow the rules listed below (otherwise excluded):

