**Applicable in all countries except the US:**

- a. Use an effective barrier method of contraception without interruption if the patient is sexually active with a FCBP. Male patients should refrain from donating sperm during the study participation and for 3 months after the last dose of study treatment, or according to the local guidelines for LEN, whichever is longer

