**Applicable in the US:**

- b. Use a latex or synthetic condom each time they have sex with a FCBP. True abstinence from heterosexual sexual intercourse is also an acceptable method of contraception. The use of emergency contraception is also permitted. Male patients should refrain from donating sperm during the study participation and for 3 months after the last dose of study drug, or according to the US guidelines for LEN, whichever is longer

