### 7.11.1 Restrictions Applicable in All Countries Except US

- All men and all women of childbearing potential should undergo counselling on the need to avoid pregnancy.
- Patients should be capable of complying with the requirements of safe use of LEN
- Patients must be provided with appropriate patient educational brochure and patient card

The following restrictions apply while the patient is receiving study treatments and for the specified times before and after:

- FCBP should use reliable methods of contraception at least 4 weeks prior to start of study treatments until 3 months after discontinuing study treatments. Acceptable methods of contraception include true abstinence, implant, tubal ligation, levonorgestrel releasing intrauterine system, medroxyprogesterone acetate depot, ovulation inhibitory progesterone-only pills (i.e., desogestrel) and vasectomized partner (vasectomy must have been confirmed by two negative semen analyses). All these methods of contraception should be used in combination with the use of a condom by their male sexual partner for intercourse

Note: implants and levonorgestrel-releasing intrauterine systems are associated with an increased risk of infection at the time of insertion and irregular vaginal bleeding. Prophylactic antibiotics should be considered particularly in patients with neutropenia.

- True abstinence is part of the preferred and usual lifestyle of the patient. Periodic abstinence (e.g., calendar, ovulation, symptothermal, post-ovulation methods), declaration of abstinence for the duration of exposure to the investigational product, and withdrawal are not acceptable methods of contraception. If FCBP wish to become pregnant they should be advised to arrange for the freezing of oocytes prior to the start of study treatment
- Male patients should avoid unprotected sex with a FCBP during treatment with the study treatments and for a washout period of 3 months. Patients should refrain from donating sperm from the start of dosing until 3 months after discontinuing study treatments. If male patients wish to father children, they should be advised to arrange for freezing of sperm samples prior to the start of study treatment

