### 10.1 Sample Size Determination

As this is a Phase 1b/2 study, Primary, Secondary [REDACTED] endpoints will be analyzed using descriptive statistics. No formal statistical tests will be performed.

[REDACTED]

Primary completion analysis and final analysis are planned to be performed. Details will be provided in the SAP.

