### 12.13.2.2 Female Patients

Female patients of childbearing potential are eligible to participate if they agree to use a highly effective method of contraception consistently and correctly as described in the [Table 13-1](#) below. Contraception guidance is to be followed during the time frame in [Section 6.1](#) on inclusion criteria. Refrain from donating eggs during the same time period.

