**Table 13-1: Highly Effective Contraceptive Methods**

Highly Effective Contraceptive Methods That Are User Dependenta Failure rate of < 1% per year when used consistently and correctly.

Combined (estrogen and progestogen containing) hormonal contraception associated with inhibition of ovulationb
 
 
• Oral
 
• Intravaginal
 
• Transdermal
 

Progestogen only hormonal contraception associated with inhibition of ovulation
 
 
• Oral
 
• Injectable
 

Highly Effective Methods That Are User Independenta

Implantable progestogen only hormonal contraception associated with inhibition of ovulationb
 
 
• Intrauterine device
 
• Intrauterine hormone-releasing system
 
• Bilateral tubal occlusion
 

Vasectomized partner A vasectomized partner is a highly effective contraception method provided that the partner is the sole male sexual partner of the FCBP and the absence of sperm has been confirmed. If not, an additional highly effective method of contraception should be used.

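### Appendix 13 contradicts the contraception eligibility criteria for men in all regions and for women in the US

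*Protocol*

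**What the plan says.** Contraception rules stand in three parts of the protocol: exclusion criteria 7 and 8 (in the synopsis and again in Section 6.2), the restrictions in Section 7.11, and Appendix 13 (Section 12.13). Exclusions 7 and 8 state that a patient who does not follow them is excluded, and Section 6 does not permit waivers. Appendix 13 is also worded as a condition of eligibility.

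*Men.* Outside the US, exclusion 8a reads "Use an effective barrier method of contraception without interruption if the patient is sexually active with a FCBP". In the US, exclusion 8b reads "Use a latex or synthetic condom each time they have sex with a FCBP", with true abstinence also accepted. Section 12.13.2.1 in Appendix 13 offers a man with a partner of childbearing potential two options: long-term abstinence, or "Agree to use a male condom plus partner use of a contraceptive method with a failure rate of < 1% per year".

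*Women.* In the US, exclusion 7h requires a woman to avoid pregnancy "by using at the same time 2 effective methods of contraception, at least one highly effective method and one additional effective method". It refers to Appendix 13 and also accepts true abstinence. Section 12.13.2.2 in Appendix 13 says that female patients of childbearing potential are "eligible to participate if they agree to use a highly effective method of contraception consistently and correctly". Outside the US, exclusion 7d asks for highly effective contraception or abstinence. Section 7.11.1 lists methods for these women and adds "All these methods of contraception should be used in combination with the use of a condom by their male sexual partner for intercourse".

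**The concern.** Both the exclusion criteria and Appendix 13 decide who may enter, so a difference between them is a difference in eligibility. The appendix is hard to set aside as background. Section 7.11 says that a teratogenic effect can be expected if lenalidomide is taken in pregnancy, and it contraindicates the drug in women of childbearing potential unless the pregnancy-prevention conditions are met, pointing to Appendix 13 for them.

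A site that works from one text could enrol a patient whom the other text would not admit. Either protection against fetal exposure then falls below what one part of the protocol demands, or the enrolment may be judged an entry-criteria deviation, a category that SAP Section 6.3 tabulates. Which of these applies would depend on the text the site or the deviation review uses.

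**Working it through.** No arithmetic is involved. The check is a side-by-side reading for each sex and region.

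| Group | Exclusions 7 and 8 | Section 7.11 | Appendix 13 |
|---|---|---|---|
| Men, outside US | 8a: barrier method if sexually active with a woman of childbearing potential; nothing on her method | 7.11.1: avoid unprotected sex; nothing on her method | Abstinence, or condom plus partner method with failure rate below 1% per year |
| Men, US | 8b: condom or true abstinence; nothing on her method | 7.11.2: the same | As above; no regional split |
| Women, US | 7h: two methods at once, or true abstinence | 7.11.2: the same | One highly effective method |
| Women, outside US | 7d: highly effective contraception or abstinence | 7.11.1: partner condom should be added to the listed methods | One highly effective method |

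Two test cases follow.

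1. A man in any region uses a condom, and his partner uses no method with a failure rate below 1% per year. He passes exclusion 8 and meets Section 7.11. He is not eligible under Appendix 13.
2. A woman in the US uses one highly effective method and nothing else. She is eligible under Appendix 13 and excluded under 7h.

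The two conflicts run in opposite directions: the appendix is the stricter text in case 1 and the looser one in case 2. Of the 2 × 2 = 4 sex-by-region groups, 3 have conflicting eligibility texts.

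The pointer from 7h to the appendix does not settle case 2. Table 13-1 covers only highly effective methods; the additional effective methods that 7h needs are listed only in Section 7.11.2. Note b to Table 13-1 asks for two highly effective methods, but only where hormonal contraception may interact with study treatment, which is a different rule from 7h.

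Both the male and female parts of Appendix 13 take their time frame from Section 6.1. That section has no contraception text; the criteria are in Section 6.2. For men even Section 6.2 leaves a gap, because 8a and 8b attach the 3-month post-treatment period to sperm donation. The post-treatment contraception period for men appears only in Section 7.11.

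**The case against.** The strongest reply is that the numbered criteria govern. Section 6 requires patients to meet them, 7h is one of them, Section 7.11.2 repeats its rule, and the appendix is titled as guidance. On that reading a US woman on one method simply fails 7h. This is a workable reading, but the protocol does not state it, and Section 7.11 refers to the appendix for conditions on which lenalidomide may be given. Applied to men, it would also remove the partner-method requirement, which Appendix 13 states as a condition of eligibility.

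A second reply is that 8a and 8b are merely silent about the partner, so every text can be satisfied together by meeting the more demanding one. That is true, and it limits the harm. But nothing tells sites to do this, and the set of eligible patients still depends on the text consulted.

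A third reply is that other safeguards exist: scheduled pregnancy tests, repeated counselling, and a patient brochure and card. They reduce the consequences but do not decide eligibility.

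Three stronger readings are tempting and are not supported.

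- A reader might infer a third opposite-answer case: a woman outside the US on a combined pill without a partner condom, since Table 13-1 lists "Combined (estrogen and progestogen containing) hormonal contraception associated with inhibition of ovulation" and Section 7.11.1 does not. But 7d and Appendix 13 agree that one highly effective method is enough for entry. Section 7.11.1 is a recommendation-type restriction outside the eligibility criteria, and its list is worded as open. What remains is a lesser mismatch over the partner condom.
- The mini-pills ruled out for the US in Section 7.11.2 may seem to clash with the oral progestogen-only methods in Table 13-1. The table limits these to products that inhibit ovulation, a type that Section 7.11.1 also names separately.
- Section 7.8.5 asks for caution with oestrogen-containing therapy in patients on lenalidomide. Caution after a benefit-risk assessment does not contradict appearing on a list of accepted methods.

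**Conclusion.** The point holds for two groups: men in all regions, and women in the US. For each, one eligibility text admits a patient whom the other does not, with no rule of precedence and a time-frame reference that leads to the wrong section. For women outside the US there is only a non-eligibility mismatch between Section 7.11.1 on one side and 7d and Appendix 13 on the other.

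The conclusion rests on reading Appendix 13 as applying in every region, since it makes no regional distinction, and on taking its eligibility wording at face value. The documents do not say how many of the approximately 51 patients are men with a partner of childbearing potential or US women of childbearing potential. They also do not show that sites have acted differently; that is a risk, not a finding.

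The sample size, estimands and planned analyses are untouched, and the protocol states "No formal statistical tests will be performed". The only link to the analysis is the count of entry-criteria deviations. The reason to act is patient safety with a drug that the protocol itself calls teratogenic.

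**What to change.** Reconcile exclusions 7 and 8 (synopsis and Section 6.2), Sections 7.11.1 and 7.11.2, and Appendix 13 so that each combination of region and sex has one rule. That rule should state the number of methods, the accepted methods, any requirement on the partner, and the duration. Within this:

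- settle whether a partner method is a condition of entry for men, and how many methods are required of US women;
- align Section 7.11.1 with 7d and Appendix 13 on the partner condom for women outside the US;
- make the Appendix 13 time-frame reference point to the section that holds it, and state the men's post-treatment contraception period there;
- make the reference in 7h lead to a list that includes the additional effective methods.

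The sponsor must decide the content; nothing here says which version is right. The cost is protocol wording, with no new procedure or data. Some sites may have to counsel patients again. Whether consent wording must also change cannot be judged, because the consent pages are not available.
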